After consenting to study participation, patients will complete a brief demographic questionnaire (see Appendix A). Additional patient data (cancer type, chemotherapy regimen, transplant type, unit of hospitalization) will be collected from the electronic medical record by a study team member. Patients will be asked what symptom they find most concerning (nausea/vomiting or anxiety) and will then be randomly assigned to the intervention or control group using a random number table based on symptom of concern. After random assignment, the patient will be educated on how to use a symptom journal (Appendix B) by a study team member and will be asked to complete the baseline symptom measures in the journal. Patients will be instructed to complete the same symptom measures on the following day independently (24 hour follow up). Patients assigned to the intervention group will receive 48 hours (6 patches) worth of essential oil infused (lavender, peppermint, or mandarin) patches. Aromatherapy patches will be applied to the patient's skin containing peppermint, mandarin, or lavender essential oils. Patient indicating that nausea/vomiting is their symptom of concern will receive peppermint as the default oil or mandarin oil if they have a known intolerance to peppermint. Patients indicating that anxiety is their symptom of concern will receive lavender oil. Patients assigned to the control group will receive 48 hours (6 patches) worth of non-scented patches (i.e., blank hydrogel adhesive patches without essential oil infusion). Patients in both groups will be instructed to change the aromatherapy patch (essential oil infused [intervention group] or non-scented [control group]) every 8 hours, as recommended by manufacturer, and document the

patch change in the symptom journal. Patients in both groups will also be instructed to remove the aromatherapy patch and contact the study team with and signs/symptoms of sensitivity to the patch adhesive or essential oil. The study team will post an “aromatherapy in use” sign inside the patient room to notify clinicians that the patient is on study, with instructions to remove the aromatherapy patch before a MRI test.

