The study team initial visit will be at 0 hours (visit 1) and follow-up visits will be completed at 24 hours (visit 2) and 48 hours (visit 3). During visit 2 (Monday-Friday only), the study team will remind participating patients to complete their symptom journal, will answer any study-related questions, and will inquire about any aromatherapy side effects. During visit 3, a study team member will instruct the patient to complete the 48-hour symptom measures in the journal and will complete a brief intervention satisfaction questionnaire (Appendix C) with the patient (intervention group only). Patients will be provided a \$25 gift card to show appreciation for their time in the study. After symptom data collection is completed, a study team member will review and document antiemetic medication administration from the electronic medical record during the 48-hour intervention time frame. **Antiemetic administration will be captured on an Excel spreadsheet on a secure Microsoft Team for intervention and control participants in the nausea/vomiting symptom group. Included medications are scopolamine, lorazepam, promethazine, prochlorperazine, olanzapine, dexamethasone, Marinol, and ondansetron indicated for nausea/vomiting. Medication type, dose, order type (scheduled vs. PRN), and number of doses will be documented for antiemetics administered during the study timeframe.** Concomitant medications (e.g., antiemetic medications, steroids, benzodiazepines) will not be controlled as part of the study as the intent is not to alter standard practice for symptom treatment, but rather to provide an adjuvant to help reduce symptom burden. However, it is reasonable to expect that the need for PRN (available as needed) medications prescribed for nausea/vomiting or anxiety may be less in the treatment group compared to control during the 48 hours of inhaled aromatherapy. Because antiemetic and benzodiazepine medications may contribute to an increase in fall risk (Seppala et al., 2018; Wildes et al., 2018), we also plan to observe fall events during the study timeframe. Unit fall total numbers and incidence data will additionally be obtained from data reported to the National Database for Nurse Quality Indicators (NDNQI) for 12 months prior to implementation and 12 months during study implementation.

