8.0 Study Calendar

	Screening	Visit 1	Visit 2 *M-F only	Visit 3	Secondary Data
	Day- Admission	Day 4-8 (0-hours)	Day 5-9 (24-hours)	Day 6-10 (48-hours)	Post Study
STUDY PROCEDURES					
Screen new admissions for inclusion/exclusion criteria	x				
Consent		x			
Demographic Questionnaire		x			
Symptom Assessment Tools		x	x	x	
Apply Patch		x			
Satisfaction Questionnaire- Intervention Group				x	
Remove Patch				x	
Evaluate Antiemetic Use					x
Evaluate Falls					x

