9.0 Reportable Events

Inhaled essential oils including lavender, peppermint, and mandarin are generally considered safe if used as indicated. The essential oils used in this study are infused within an adhesive patch, so will not come in direct contact with the skin. However, if the essential oil patch is used not as indicated (e.g. oil applied directly to the skin, oil ingested), the risk of adverse event occurrence may increase.

Adverse Event: Defined as any problematic medical occurrence in a study participant who has received the intervention including inhaled lavender, peppermint, or mandarin essential oil, regardless of possibility of a causal relationship. Adverse events will be documented after the participant begins receiving the intervention.

The occurrence and nature of each participant's medical condition will be documented by study personnel prior to enrollment. Study personnel will document any changes in medical condition and/or the occurrence and description of any adverse event during the study. Events that occur from inhaled essential oil administration up to 72 hours after will be recorded (allows for 24 hours of monitoring after intervention ends). Events will be reviewed during data safety monitoring to determine causality.

Significant Adverse Event: Defined as a life-threatening condition (i.e. immediate risk of dying); severe/permanent disability; a significant hazard, contraindication, side effect, or precaution as deemed by the Data Safety Monitoring team to be caused by the intervention. Investigators will determine causality based on the participant's clinical course, medical history, and administered medications.

Adverse and Significant Adverse Events will be reported to the IRB within 5 business days from discovery if they are determined to be (1) unexpected; (2) related or possibly related to participation in the study; (3) finding suggests that the research procedures involve a greater harm risk than previously anticipated; (4) occurrence of unanticipated adverse device effects.

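### Section 9 sets a 72-hour adverse-event window, but sections 7 and 8 schedule a side-effect enquiry only at 24 hours, on weekdays, and no contact or adverse-event record review for hours 48 to 72

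*Combined protocol and SAP*

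**What the plan says.** Section 9.0 (Reportable Events) fixes the recording period: "Events that occur from inhaled essential oil administration up to 72 hours after will be recorded (allows for 24 hours of monitoring after intervention ends". It defines an adverse event broadly, without requiring a causal link, but only in participants who received the essential-oil intervention. It also gives study personnel a general duty to document changes in medical condition and adverse events while the study runs.

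Section 7.0 (Study Procedures) gives the exposure as "48 hours (6 patches) worth of essential oil infused" patches, changed "every 8 hours, as recommended by manufacturer". On contacts it says "follow-up visits will be completed at 24 hours (visit 2) and 48 hours (visit 3"). Asking about aromatherapy side effects is listed under Visit 2, which is held Monday to Friday only. At Visit 3 the patient completes the symptom measures, and the team member "will complete a brief intervention satisfaction questionnaire (Appendix C) with the patient (intervention group only"). Afterwards "a study team member will review and document antiemetic medication administration from the electronic medical record during the 48-hour intervention time frame"; the data capture is described for the nausea/vomiting group.

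In section 8.0 (Study Calendar) the last visit column is "Day 6-10 (48-hours"). The Secondary Data column that follows lists antiemetic use and falls. There is no adverse-event row and no 72-hour entry.

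**The concern.** A recording window is only as good as the contacts or sources that fill it. Section 9.0 speaks of monitoring for a day after the patches end, yet the procedures and calendar contain nothing that would carry this out. The one planned question also comes halfway through exposure, so the second half of patch wear has no listed enquiry either.

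At stake is the completeness of the safety data. An event in the second day of wear or in the day after removal could go unrecorded, and its absence would look the same as no event. How much is found would depend on how each team member reads the general duty in section 9.0.

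**Working it through.** **Inputs.** Six patches, 8 hours each, visits at 0, 24 and 48 hours, and the side-effect enquiry at Visit 2 on weekdays (section 7.0); calendar rows and columns (section 8.0); a 72-hour window with 24 hours after the intervention (section 9.0).

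**Step 1: reproduce the plan's figure.** 6 patches × 8 h = 48 h of intervention; 48 h + 24 h = 72 h. The window reproduces, and the clock evidently runs from the first patch.

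**Step 2: lay the schedule over the window.**

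| Hours | Patches | Side-effect enquiry covering the period | Visit at end of period | Record review described |
|---|---|---|---|---|
| 0–24 | 1–3 | Visit 2, weekdays only | Visit 2, weekdays only | Antiemetics |
| 24–48 | 4–6 | None listed | Visit 3 | Antiemetics |
| 48–72 | None | None listed | None | None |

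**Step 3: size of the gap when Visit 2 takes place.**
- No scheduled side-effect enquiry: 72 − 24 = 48 h; 48/72 = 67%. This includes 48 − 24 = 24 h of patch wear (24/8 = 3 of the 6 patches) and all 24 post-intervention hours.
- No scheduled contact of any kind: 72 − 48 = 24 h; 24/72 = 33%.

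**Step 4: effect of the weekday restriction.** Visit 2 falls one day after the start. A Friday start puts it on Saturday and a Saturday start on Sunday, and no substitute is described. Those participants have no scheduled enquiry in any of the 72 hours. That is 2 of 7 possible start days. If starts were spread evenly over the week, which is an assumption, it would be 2/7 = 29% of participants. If nobody started at a weekend, only Friday would matter, 1/5 = 20% on the same even-spread assumption. The protocol does not give the distribution of start days.

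**Step 5: what the other routes reach.**
- Participants in both groups are told to remove the patch and call the team about a reaction to the adhesive or oil (section 7.0). Other kinds of event are not mentioned.
- Patch removal is marked at Visit 3 (section 8.0), so a skin reaction might be noticed then. Nothing is marked after it.
- Appendix C opens with a general question about the experience. It is put to the intervention group only, at 48 hours, and cannot reach hours 48–72.
- Fall events are to be observed during the study, but the source described is unit totals, and falls are one type of event.
- The weekly team review (section 10.0) and the entry of serious events after notification (section 10.0, Oncore Safety Reporting) act on events already known.
- The section 9.0 documentation duty covers the whole period but names no contact, source or time point.

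**The case against.** The best case for the plan is that a missing scheduled question is not missing detection. Section 9.0 obliges staff to document events, participants are inpatients with a sign in the room, both groups are told to report sensitivity, patches come off at Visit 3, and the intervention group gets an open question at 48 hours. Nothing prohibits a chart check for adverse events. The study is described as minimal risk, safety is not among its objectives or outcomes, and section 12.0 plans no adverse-event analysis.

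Much of this stands, and it rules out several stronger readings that a reader might infer:
- That most of the window has no means of detection. The routes above exist; what is missing is a scheduled or specified one after 24 hours.
- That all chart review stops at 48 hours. The review is done after the visits; only its antiemetic data frame ends at 48 hours.
- That the gap is the same for everyone. It depends on the start day.
- That the sample journal proves the point because it shows no side-effect field. Appendix B is a sample with a placeholder where the measurement tool goes, so it cannot show what the final journal lacks.
- That an unsupported 72-hour tolerability claim is planned. No such statement is announced.

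The objection does not remove the mismatch. Section 9.0 says that a period is monitored, and sections 7.0 and 8.0 list nothing that monitors it.

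**Conclusion.** The point holds as an inconsistency between a stated monitoring period and the scheduled means of filling it. After 24 hours (48 of 72 h, 67%), or over the whole window for Friday and Saturday starters, ascertainment rests on spontaneous reports, incidental observation at Visit 3, or a duty with no named method. For the last 24 hours (33%) there is no scheduled contact at all.

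This assumes that the procedures listed in sections 7.0 and 8.0 are the ones carried out, and that a Visit 2 due at a weekend is not replaced. The share of participants affected by the weekday rule cannot be fixed from the documents. The number of events that would be missed cannot be estimated either, since no event rate is given. The consequence is confined to the safety data. It should be corrected, but it does not threaten the trial's main comparison.

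**What to change.** Reconcile sections 7.0, 8.0 and 9.0 so that the stated window has a stated method:

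1. Add the side-effect enquiry to the existing Visit 3, asking about the whole period since the first patch. It then also serves participants whose Visit 2 falls on a weekend. Visit 3 carries no weekday restriction in the plan; the amendment should confirm that it takes place at weekends.
2. Extend the post-study electronic record review to look for adverse events from first patch to 72 hours, in the anxiety group as well as the nausea/vomiting group. Section 1.0 describes stays of four weeks or more, so inpatient records should usually cover hour 72.
3. Add an adverse-event row to the calendar, marked at Visit 2, Visit 3 and Secondary Data (to 72 hours).
4. Decide whether events are to be collected in the control arm, which also wears adhesive patches. If so, amend the section 9.0 definition, which now covers only participants who received the intervention.

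The cost is a few minutes at a visit that already exists, a longer record review that now takes in the anxiety group, and amendments to sections 7.0 and 8.0, plus 9.0 if control-arm events are collected. No new visit is needed.

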10.0 Data Safety Monitoring

The study investigator will meet with study key personnel to review data quality, subject recruitment, accrual, retention, and outcome and adverse event data. Study team review will occur on a weekly basis to provide monitoring updates and discuss safety/quality concerns. If an adverse event occurs in which causality cannot be determined by the research team, the study investigator will consult with the patient's medical team to clarify/confirm event causality. Based on findings from the weekly review, considerations for protocol adjustment will be made in the event that opportunities are identified to improve participant safety and/or data quality.

This study will be conducted in accordance with the IU Simon Cancer Center Institutional DSMP for **Low Risk Trials**.

Investigators will conduct continuous review of data and subject safety. Quarterly review meetings for low risk trials are required and will include the principal investigator, clinical

research specialist and/or research nurse (other members per principal investigator's discretion). Quarterly meeting summaries should include review of data, the number of subjects, significant toxicities as described in the protocol, and responses observed. Study teams should maintain meeting minutes and attendance for submission to the DSMC upon request.

Data and Safety Monitoring Committee

The IUSCC Data and Safety Monitoring Committee (DSMC) is responsible for oversight of subject safety, regulatory compliance, and data integrity for this trial. The DSMC will review this study annually to review overall trial progress, toxicity, compliance, data integrity, and accrual per the Institutional DSMP.

Furthermore, the DSMC conducts an administrative review of serious adverse events (SAEs), deviations, reportable events, and any other outstanding business. Major issues may require further DSMC review or action.

At any time during the conduct of the trial, if it is the opinion of the investigators that the risks (or benefits) to the subject warrant early closure of the study, the DSMC Chair and Compliance Officer must be notified within 1 business day via email, and the IRB must be notified within 5 business days. Alternatively, the DSMC may initiate suspension or early closure of the study based on its review.

Study Auditing and Monitoring

All trials conducted at the IUSCC are subject to auditing and/or monitoring per the Institutional DSMP. Reports will be reviewed by the full DSMC at the time of study review.

Data Management/ Oncore Reporting Requirements

The DSMC reviews data and study progress directly from Oncore; therefore, timely data entry and status updates are vital. Study data must be entered within Oncore promptly, no later than one week from study visit occurrence. Subject status in Oncore will be updated in real time, as this may affect overall trial enrollment status. Global SAEs and deviations will be reviewed on a monthly basis by the DSMC Chair directly from Oncore.

Study Accrual Oversight

Accrual data will be entered into the IU Simon Cancer Center OnCore system. The Protocol Progress Committee (PPC) reviews study accrual twice per year, while the PPC coordinator reviews accrual quarterly.

Oncore Safety Reporting

In addition to protocol- and regulatory-required safety reporting, all serious adverse events (SAEs) will be captured in the Oncore system within 1 business day of notification. Initial SAE reporting will include as much detail as available, with follow-up to provide complete

information. Attributions will be assessed to study drugs, procedures, study disease, and other alternate etiology.

Protocol Deviation Reporting

Protocol deviations will be entered into OnCore within 5 days of discovery and reviewed by the DSMC Chair on a monthly basis. Findings will be reported to the full DSMC at the time of study review. For serious or repetitive protocol deviations, additional action may be required by the DSMC.

11.0 Study Withdrawal/Discontinuation

Participants may withdrawal anytime by notifying the principle investigator ([name]) or any other member of the study team. Choosing not to participate or withdrawal from the study will not influence relationships or patient status at IU Health.

12.0 Statistical Considerations

SAS and/or R statistical packages will be used to analyze primary outcomes, secondary outcomes, and demographic sample data.

Primary Outcomes

Comparisons between the intervention and control groups for differences in the CINVR and anxiety tools will be analyzed using mixed-model ANOVA, with time (baseline, 24 hours, 48 hours) repeated within subject. Chi-square tests will be used to compare the groups for differences in the proportions of patients prescribed medications for nausea/vomiting or anxiety. Separate analyses will be performed for the two symptom groups. A two-sided 5% significance level will be used for all tests.

Sample size justification: With sample sizes of 50 patients within each symptom group, 25 intervention/25 control within each symptom group, the study will have 80% power to detect an effect size of 0.81 between intervention and control within each symptom group, based on a two-sample t-test calculation and a two-sided 5% significance level. The recruitment target will be 112 participants (56 per symptom group) to account for a 10% drop out rate.

Secondary Outcomes

Descriptive statistics will be used to analyze frequencies and percentages of the patient satisfaction questionnaire responses, documented antiemetic administration, and number of unit falls. The number of (1) total antiemetic medication doses and (2) doses for each individual medication (i.e., Ativan, promethazine) will be compared between the control and intervention groups for the nausea/vomiting symptom group. The percentage change for number of falls will be calculated by comparing number of falls 12 months prior to intervention implementation to 12 months during implementation.

Descriptive statistics will be used to summarize the demographics of the study sample (frequencies and percentages for categorical variables, means and standard deviations for continuous variables).

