3.0 Outcome Measures

3.1 Primary Outcome Measures

Chemotherapy-Induced Nausea, Vomiting and Retching (CINVR)

CINVR involves three distinct gastrointestinal symptoms (nausea, vomiting, retching) influenced by administration of chemotherapy. Nausea is expressed as an unpleasant

feeling in the throat/epigastrium that can result in expulsion of stomach content, known as vomiting (Rhodes VA, 2001). Retching is the effort to expel stomach contents without success (Rhodes VA, 2001). A review of CINVR instruments identified the Rhodes Index of Nausea, Vomiting and Retching (INVR) was the only instrument that separately assesses all three symptoms (Wood et al., 2011). The INVR will be used to measure CINVR and includes 8 Likert-type items on a 5-point scale, with evidence supporting reliability (Spearman correlation 0.87) and validity (Rhodes & McDaniel, 1999). Completion of the tool will occur at baseline, 24 hour, and 48 hours of intervention.

The primary endpoint for CINVR is the mean INVR score change from (1) baseline to 24 hours and (2) baseline to 48 hours. We anticipate a 30% reduction in the INVR mean score for participants randomized to the intervention group who indicated nausea/vomiting as primary symptom of concern.

Anxiety

Anxiety is excessive or persistent worry about aspects of life ("Understanding the Facts of Anxiety Disorders and Depression is the First Step," n.d.). Anxiety will be measured using a shortened version of Spielberger's State Anxiety Inventory (SAI). The original SAI contains 20 items to measure state anxiety and items are scored using a 4-point Likert-type scale (almost never-almost always) (Spielberger, Gorsuch, Lushene, Vagg, & Jacobs, 1983). The SAI instrument has good internal consistency (.86-.95), test-retest reliability (.65-.75) (Spielberger et al., 1983), and evidence supporting construct and concurrent validity (Spielberger et al., 1983). The shortened SAI retains 6 items (from the original 20) and has evidence supporting good internal reliability consistency (Cronbach's alpha .84) and strong construct validity (Abed, Hall, & Moser, 2011). Completion of the tool will occur at baseline, 24 hours, and 48 hours of intervention.

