The primary endpoint for anxiety is the mean shortened SAI score change from (1) baseline to 24 hours and (2) baseline to 48 hours. We anticipate a 30% reduction in the SAI mean score for participants randomized to the intervention group who indicated anxiety as their primary symptom of concern.

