5.0 Study Design

This study will be a randomized controlled trial. Prior to randomization, participants will be asked which symptom, nausea/vomiting or anxiety, is most burdensome for them. Participants will be stratified based on their identified symptom of burden (nausea/vomiting or anxiety) and will then be randomized to either the intervention or control group, with a target of 50 participants in the nausea/vomiting symptom group (25 intervention and 25 control) and 50 participants in the anxiety symptom group (25 intervention and 25 control). Intervention and control groups will receive Wyndmere Naturals, Inc. aromatherapy patches and a symptom journal. Participants in the intervention group indicating that nausea/vomiting is the primary symptom of concern will receive peppermint inhaled aromatherapy patches (or mandarin if peppermint intolerance indicated). Participants in the intervention group indicating that anxiety is the primary symptoms of concern will receive lavender inhaled aromatherapy patches. The control group will receive non-scented aromatherapy patches (i.e., blank hydrogel adhesive patches without essential oil infusion), so it will not be feasible to blind participants to group assignment. The control group will have the same interactions with the study team as the intervention group and will complete patch changes and a symptom journal to serve as an attention control.

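### The primary mixed-model ANOVA is valid but leaves an already collected baseline unused as an adjuster, and it does not name the test for the two listed changes

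*Combined protocol and SAP*

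**What the plan says.** Section 12.0 states that differences between intervention and control on the two tools "will be analyzed using mixed-model ANOVA, with time (baseline, 24 hours, 48 hours) repeated within subject". The two symptom groups are analyzed separately, and every test is two-sided at 5%. The section mentions no baseline covariate and no constraint that the arms have equal means at baseline. It names no model term or contrast as the primary test.

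Section 3.1 defines each endpoint as a pair of changes and ranks neither: "The primary endpoint for CINVR is the mean INVR score change from (1) baseline to 24 hours and (2) baseline to 48 hours", and likewise "The primary endpoint for anxiety is the mean shortened SAI score change from (1) baseline to 24 hours and (2) baseline to 48 hours".

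The sample-size paragraph of section 12.0 says that with 25 per arm "the study will have 80% power to detect an effect size of 0.81 between intervention and control within each symptom group", from a two-sample t-test. It does not say whether 0.81 is in SDs of the score or of the change.

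In section 7.0, random assignment comes first, and the patient then "will be asked to complete the baseline symptom measures in the journal". Section 5.0 explains that control patches are unscented, "so it will not be feasible to blind participants to group assignment".

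**The concern.** A model that holds baseline as a free outcome level estimates the treatment effect as follow-up minus baseline, compared between arms. Baseline noise is then subtracted at full weight. Using baseline as a covariate gives it the weight the data support, which lowers the variance. With only 25 per arm, that gain is worth having.

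The second gap is that two changes are listed and no term is named. The quoted 80% power belongs to a single comparison, and the plan does not say which. A reader cannot tell whether success means the interaction, one change, either change or both, so the choice could be made after the data are seen.

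**Working it through.** **Inputs.** From section 12.0: 25 per arm, effect 0.81, two-sided 5%, 10% dropout. Assumed, because the documents do not give them: a common correlation ρ among the three times (0.3 / 0.5 / 0.7), equal SDs at all three times, normal scores and complete data. The nearest figure in the documents is the test-retest reliability of .65 to .75 for the original 20-item anxiety inventory (section 3.1). It is illustrative only.

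**1. The plan's own figure.** The noncentrality is 0.81 × √(25/2) = 2.86. With 48 df, power is 80.1%, and the effect detectable at 80% is 0.809. Recruitment is 50/0.9 = 55.6, so 56 per symptom group and 112 in all. Both stated figures reproduce.

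**2. Variance.** In units of the score variance, the change has variance 2(1−ρ) and the baseline-adjusted score has 1−ρ². Their ratio is 2/(1+ρ) = 1.54 / 1.33 / 1.18, or 1.21 to 1.14 at ρ = 0.65 to 0.75.

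**3. Power at 48 hours** (noncentral t). The unadjusted test has 48 df. The adjusted test has 47 df, with variance multiplied by 1 + 1/46 for chance baseline imbalance.

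| Meaning of 0.81 | Test | Standardized effect at ρ = 0.3 / 0.5 / 0.7 | Power |
|---|---|---|---|
| Score SDs | Unadjusted: 0.81/√(2(1−ρ)) | 0.685 / 0.810 / 1.046 | 66.0 / 80.1 / 95.2% |
| Score SDs | Adjusted: 0.81/√((1−ρ²)(1+1/46)) | 0.840 / 0.925 / 1.122 | 82.9 / 89.3 / 97.3% |
| Change SDs | Unadjusted | 0.81 throughout | 80.1% |
| Change SDs | Adjusted: 0.81 × √(2/(1+ρ))/√(1+1/46) | 0.994 / 0.925 / 0.869 | 93.1 / 89.3 / 85.3% |

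Simulation agrees: 83.1 / 89.1 / 97.3% and 93.2 / 89.2 / 85.4% for the adjusted rows. At ρ = 0.65 to 0.75, on the change-SD reading, adjusted power is about 86 to 84%.

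**4. Unequal SDs.** Let the follow-up SD be k times the baseline SD. The ratio of unadjusted to adjusted variance is (1 + k² − 2ρk) / (k²(1−ρ²)).

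| ρ | k = 1.3 | k = 1.0 | k = 0.7 |
|---|---|---|---|
| 0.5 | 1.10 | 1.33 | 2.15 |
| 0.7 | 1.01 | 1.18 | 2.04 |

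The numerator exceeds the denominator by (1−ρk)², which is never negative. In large samples adjustment therefore cannot lose precision, but the gain can nearly vanish or take the variance ratio to about 2.

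**5. Which test.** With an unconstrained baseline, the group-by-time interaction is the joint test of the two listed changes. Under equal correlation, the two changes correlate (1−ρ)/(2(1−ρ)) = 0.5. With 0.81 change SDs at both times, the noncentrality is 12.5 × 0.81² × 2/1.5 = 10.9. On F(2, 47) this gives about 82% power at 5% error. Other rules behave differently:
- Either change at 5% suffices: error is 9.1% per symptom group (bivariate normal, correlation 0.5).
- Both changes are required at 5%: power is about 69% when both effects are 0.81 change SDs.

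**6. The joint test with adjustment.** For 0.81 score SDs at both times, power is 68 / 82 / 97% unadjusted and 92 / 94 / 99% adjusted (simulated).

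**The case against.** The strongest reply is that nothing is broken. The endpoint is change, the planned model estimates change, and a statistician reading a two-group ANOVA with repeated times would test group-by-time. That is one 5% test per symptom group, and it meets the planned power. This stands. A reader might infer from the two unranked changes that the trial runs a 9% error rate or has only 69% power. The documents do not support that, because each figure needs a success rule that no section states. What remains is that the term should be named.

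A second reply is that adjustment is a preference, and that the larger gains come from assuming ρ = 0.3. This stands in part. Near the only correlation-like figure in the documents, the 48-hour gain on the change-SD reading is from 80% to about 84 to 86%. The gain also depends on equal SDs, which short bounded scales may not show. Still, the baseline is collected anyway, and in large samples adjustment does not lose precision.

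A reader might also infer that baseline scores are biased by knowledge of the arm. Section 7.0 puts baseline after assignment but does not say whether participants know their arm by then, and it describes the patches only after the baseline measures. The bias is possible, not shown. If baseline in one arm shifted by b, the change would be biased by b and the adjusted difference by ρb, so adjustment reduces this bias but does not remove it.

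**Conclusion.** The point holds as a low-cost improvement in efficiency plus a missing specification. The planned test is not invalid. Under the stated assumptions, 48-hour power rises from 66 / 80 / 95% to 83 / 89 / 97% (score SDs) or from 80% to about 93 / 89 / 85% (change SDs) at ρ = 0.3 / 0.5 / 0.7. The gain is small when ρ is high, and it moves widely if the SDs differ between times. The 66% is not a finding that the trial is underpowered: it needs both ρ = 0.3 and the score-SD reading, and the documents give neither. Read as the group-by-time test, the plan keeps 5% error and about 82% power at 0.81 change SDs. It should say that this is the test, and which SD the 0.81 refers to.

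**What to change.** 1. In section 12.0, within each symptom group, model the 24- and 48-hour scores of the matching tool with group, time, group-by-time, baseline score and baseline-by-time, using an unstructured covariance.
2. Name one two-sided 5% primary test per symptom group from that model. By default this is the joint 2-df test of the 24- and 48-hour group differences, with each time tested at 5% only if the joint test is significant.
3. In section 7.0, have the baseline measures completed before the assignment is disclosed. Keeping baseline as an outcome with arm means constrained equal is an acceptable alternative to item 1 only if this is done, because the constraint may be false for a baseline reported after the arm is known.
4. State whether 0.81 is in score SDs or change SDs, and to which test the 80% power applies.

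The cost is plan wording and a reordering within visit 1, with no extra data or participants. The price of item 2 is that neither single time can be claimed if the joint test fails. The joint test also relies on the 24-hour score, which patients complete on their own: "During visit 2 (Monday-Friday only), the study team will remind participating patients to complete their symptom journal". Missing 24-hour scores would lower the power figures given for it.
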